8. ANALYSIS SETS

The following subject population will be used for safety analyses:

- **Safety analysis set** will include all subjects who have received at least 1 dose of the candidate rabies mRNA vaccine CV7202 or the active control Rabipur and for whom any post-Day 1 safety data are available. The statement that a subject had no AEs (on the Adverse Event eCRF) constitutes a valid safety assessment. The analysis of safety will be performed on this population.

The following subject populations will be used for analyses of immunogenicity objectives:

- **Full analysis (FA) set** is the subset of the safety analysis set with subjects who have the baseline sample and at least 1 additional blood sample available for VNT analysis. This analysis set is the primary analysis set for all immunogenicity objectives.

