11.1 Safety Endpoints and Variables

The analysis of the primary objective to assess the safety and reactogenicity profile will examine solicited and unsolicited adverse events.

The primary endpoints include the following:

- The percentages of subjects with, and the frequencies and intensities of solicited local AEs reported on the day of vaccination and the 7 subsequent days (Days 1-8).
- The percentages of subjects with, and the frequencies, intensities, and relationship to vaccination of solicited systemic AEs reported on the day of vaccination and the 7 subsequent days (Days 1-8).
- The duration (in days) of solicited local AEs, of solicited systemic AEs, and of the individual solicited AEs.
- The percentages of subjects with and frequencies and intensities of any unsolicited and related unsolicited AEs reported on the day of vaccination and the 28 subsequent days (Days 1-29).

- The percentages of subjects with and frequencies and relationship to vaccination of any serious AEs (SAEs) and any medically attended AEs (MAAEs) up to 12 months after the last dose.
- The percentages of subjects with and frequencies and relationship to vaccination of any AEs of special interest (AESIs) up to 12 months after the last dose.

Secondary safety endpoints are:

- The percentages of subjects with and frequencies of SAEs and MAAEs related to study vaccination from 12 months after the last dose up to 24 months after the last dose (trial end).
- The percentages of subjects with and frequencies and relationship to vaccination of any AESIs from 12 months after the last dose up to 24 months after the last dose (trial end).

Further safety variables include the following:

- Extent of exposure
- Physical examination, weight, BMI
- 12-Lead electrocardiogram
- Vital signs
- Safety laboratory - hematology, biochemistry, coagulation
- Laboratory - Urine dipstick pregnancy test, serum pregnancy test (human chorionic gonadotropin)

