14.1.1 Subject Disposition by Dosage/Vaccine, All Subjects

	CV7202 1 µg	CV7202 2 µg	CV7202 5 µg	Rabipur	Total
Subjects screened					N
Subjects enrolled					x
Subjects vaccinated	xx (xx.x%)	xx (xx.x%)	xx (xx.x%)	xx (xx.x%)	xx (xx.x%)
Subjects ongoing	xx (xx.x%)	xx (xx.x%)	xx (xx.x%)	xx (xx.x%)	xx (xx.x%)
Subjects completed	xx (xx.x%)	xx (xx.x%)	xx (xx.x%)	xx (xx.x%)	xx (xx.x%)
Subjects withdrawn	xx (xx.x%)	xx (xx.x%)	xx (xx.x%)	xx (xx.x%)	xx (xx.x%)
Safety Analysis Set ^[a]	xx (xx.x%)	xx (xx.x%)	xx (xx.x%)	xx (xx.x%)	xx (xx.x%)
Full analysis (FA) set ^[b]	xx (xx.x%)	xx (xx.x%)	xx (xx.x%)	xx (xx.x%)	xx (xx.x%)
Main reason for termination	Consent withdrawn Violation of in/ex criteria Continuation jeopardizes subject Adverse event Non-compliance Lost to follow-up Study terminated by sponsor Pregnancy Other	xx (xx.x%) xx (xx.x%)	xx (xx.x%) xx (xx.x%)	xx (xx.x%) xx (xx.x%)	xx (xx.x%) xx (xx.x%)

[a] Received at least 1 dose of CV7202 or Rabipur.

[b] All subjects of the Safety Analysis Set with baseline and at least 1 postbaseline VNT sample.

Percentages are based on the number of vaccinated subjects in each column.

PROGRAM SOURCE: tlf-###, DATA CUT OFF DATE: DDMMYYYY

RUN DATE: DDMMYYYY hh:mm

Programming note:

Subjects ongoing will only be displayed, if table is generated before end of the trial.

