16.2.1.1 Subject Disposition
All Subjects

Group	Subject number	Complete subject code	Safety set [a]	FAS set [b]	Informed consent obtained on	(First) Vaccination on
-------	----------------	-----------------------	----------------	-------------	------------------------------	------------------------

[a] Received at least 1 administration of the trial product.

[b] Received at least 1 administration of the trial product and has baseline and at least 1 additional blood sample available for VNT analysis.

PROGRAM SOURCE: tlf-###, DATA CUT-OFF DATE: DDMMYYYY

RUN DATE: DDMMYYYY hh:mm

CureVac AG
CV-7202-104

Statistical Analysis Plan
24 February 2022

Sponsor
Protocol Number

Clinical Study Report
Page x of y

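### Safety-set membership depends on post-Day 1 data although the primary endpoints start on Day 1, and three shell footnotes define the set by dosing alone

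*SAP*

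**What the plan says.** SAP section 8 sets two conditions for the safety analysis set: at least one dose of CV7202 or Rabipur, and being a subject "for whom any post-Day 1 safety data are available". It adds one clarification: "The statement that a subject had no AEs (on the Adverse Event eCRF) constitutes a valid safety assessment". It then states: "The analysis of safety will be performed on this population". Protocol section 10.2 has the same definition, so the body of the SAP follows the protocol.

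The output shells describe the set differently. In Tables 14.1.1 and 14.1.2, footnote [a] to the safety set row reads "Received at least 1 dose of CV7202 or Rabipur". In Listing 16.2.1.1 it reads "Received at least 1 administration of the trial product". None of the three mentions data after Day 1.

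SAP section 12, which lists changes from the protocol's analyses, covers only the removal of the per-protocol sets.

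The endpoints themselves include Day 1. SAP section 11.1 counts solicited events from the day of vaccination through Day 8 and unsolicited events from the day of vaccination through Day 29. SAP section 11.2.3 schedules an investigator assessment of the injection site one hour after the injection, and protocol section 9.2 keeps every subject under observation for four hours.

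**The concern.** A safety population normally includes everyone exposed. Here, entry also depends on something that happens after vaccination, namely whether any safety information was obtained after Day 1. A dosed subject seen only on Day 1 has usable data for the primary endpoints, yet section 8 leaves that subject out.

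Two things are at stake. First, in a first-in-human trial with planned groups of 10 or 16, and dose-regimen subgroups of 8, one missing reactor visibly changes a reported percentage. Second, the SAP gives the programmer two definitions of one set, and nothing in the text says which governs.

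An exclusion would also be only partly traceable. The adverse event and reactogenicity tables and listings are all restricted to the safety set, so the subject's Day 1 reactions would not appear in them. Listing 16.2.3.1, which gives reasons for exclusion, has a column for the full analysis set and none for the safety set.

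**Working it through.** There is no plan figure to reproduce, because the trial has no statistical sample size (SAP section 5). The check is a comparison of text, followed by an illustration of scale.

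**Step 1: the definitions side by side**

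| Place | At least one dose | Safety data after Day 1 |
|---|---|---|
| Protocol 10.2 | required | required |
| SAP 8 | required | required |
| Tables 14.1.1, 14.1.2, footnote [a] | required | not mentioned |
| Listing 16.2.1.1, footnote [a] | required | not mentioned |

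The definitions differ for one kind of subject only: dosed, with nothing recorded after Day 1.

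**Step 2: what the nil-AE sentence does**

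The sentence treats a nil entry on the adverse event eCRF as a valid assessment. It does not say whether that entry must itself date from after Day 1. Under SAP section 11.2.1, solicited reactions reach the adverse event pages only if they are serious or still present on Day 8. A subject with a short Day 1 reaction could therefore have a nil entry and stay in the set. A subject with an adverse event recorded on Day 1 and nothing later has no equivalent route in. The relief is uneven, but it does not exclude every reactor.

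**Step 3: could such a subject exist here?**

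SAP section 6.4 describes the second interim analysis as following the vaccination of 16 + 16 + 10 + 11 = 53 subjects, with observation until Visit 12 (Day 57). If all 53 were in fact seen after Day 1, the two definitions select the same people.

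**Step 4: scale, assuming one such subject**

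Let x of n dosed subjects have the reaction.

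- If the dropped subject is a reactor, the rate falls from x/n to (x − 1)/(n − 1), a drop of (n − x)/[n(n − 1)]. With x = 1 this equals 1/n.
- If the dropped subject is a non-reactor, the rate rises from x/n to x/(n − 1), a gain of x/[n(n − 1)].

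Exact (Clopper-Pearson) 95% limits are the 0.025 quantile of Beta(x, n − x + 1) and the 0.975 quantile of Beta(x + 1, n − x), with the lower limit set to 0 when x = 0. The SAP plans no intervals for adverse event rates; these show precision only.

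| Group | All dosed | One reactor dropped |
|---|---|---|
| n = 8 (planned regimen subgroup) | 1/8 = 12.5% (0.3 to 52.7) | 0/7 = 0% (0 to 41.0) |
| n = 10 (5 µg) | 1/10 = 10.0% (0.3 to 44.5) | 0/9 = 0% (0 to 33.6) |
| n = 11 (Rabipur, as vaccinated) | 1/11 = 9.1% (0.2 to 41.3) | 0/10 = 0% (0 to 30.8) |
| n = 16 (1 µg or 2 µg) | 1/16 = 6.25% (0.2 to 30.2) | 0/15 = 0% (0 to 21.8) |

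**Step 5: direction**

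At n = 16 with one reactor, dropping a non-reactor moves 1/16 = 6.25% up to 1/15 = 6.7%. With four reactors, dropping a reactor gives 3/15 = 20.0% and dropping a non-reactor gives 4/15 = 26.7%, against 4/16 = 25.0%. The sign depends on who is lost.

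**The case against.** The strongest reply is that the rule probably excludes nobody. The SAP, dated 24 February 2022, was written after an interim analysis that it describes as covering 53 vaccinated subjects to Day 57. The protocol also works hard to obtain data after Day 1:

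- Visit 4 falls on Day 2 or 3, and the CV7202 groups have a Day 3 phone call (sections 9.4.4 and 9.4.5).
- Vaccinated subjects who stop early are to have the final-visit procedures, and at least three contact attempts are required (sections 7.2 and 7.4).
- Adverse events are followed until the outcome is known or nothing more can be learned (Appendix 11).

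A single item from any of these satisfies section 8. A subject who reacted on Day 1 may be among the most closely followed. This stands, and it is why the point is small. It does not make the case impossible: section 6.4 describes a data cut and does not show that each subject attended. Section 7.2 waives final-visit procedures that pose unacceptable risk, and it provides for replacing some subjects who drop out before Visit 4.

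A second reply is that the footnotes are shorthand. They sit on disposition outputs, while the adverse event shells name the safety set without redefining it. That is a fair reading. It weakens any inference that the adverse event tables would carry two rival denominators. The SAP still leaves the shorthand unexplained.

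A third reply is that an exclusion would be noticed. Tables 14.1.1 and 14.1.2 show vaccinated and safety-set counts on separate rows, and Listing 16.2.1.1 flags membership by subject. So the exclusion itself could be seen; the excluded subject's reactions would still be absent from the safety-set outputs.

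Finally, section 8 matches the protocol. That is correct: the SAP body is not a deviation, and the mismatch is between the body and the shells.

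**Conclusion.** The point holds in a limited form. The post-Day 1 condition does not fit primary endpoints that start on Day 1, and the SAP contains two definitions of its safety set that it does not reconcile. Followed literally, section 8 would remove a dosed subject with Day 1 data only.

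A reader might infer that the primary safety result is biased towards safety. The documents do not support that. They identify no such subject, and they do not show that early dropouts tend to be acute reactors. A dropped non-reactor would raise the rate, and the nil-AE sentence can keep a subject whose brief diary reaction never reached the adverse event eCRF. The uneven relief in that sentence makes bias towards safety plausible, but no more than that.

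The size is nil if every vaccinated subject has safety data after Day 1. If one reactor with Day 1 data only exists, and is the only reactor in the group, the reported rate falls by 1/n: 6.25 percentage points at n = 16 and 12.5 at n = 8. These figures illustrate one hypothetical subject and do not predict a result. The change is worth making because it is cheap and removes the dependence on follow-up.

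**What to change.** Redefine the safety set in SAP section 8 as everyone who was given one or more doses of CV7202 or Rabipur, analysed as vaccinated. SAP section 7 already bases analyses on the vaccine and regimen actually received. Delete the post-Day 1 condition and the nil-AE sentence, which is then unnecessary. Leave footnote [a] in Tables 14.1.1 and 14.1.2 and Listing 16.2.1.1 unchanged, since it will then be correct. Record in SAP section 12 that this departs from protocol section 10.2, with the reason.

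The full analysis set should not change in practice: it needs a further VNT sample, and the first scheduled one after baseline is on Day 8.

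The cost is one sentence in section 8 and one in section 12. No new data are needed, and no result changes if nobody has Day 1 data only.

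If the sponsor prefers to keep the protocol definition, the minimum is to correct the three footnotes, add a safety-set column to Listing 16.2.3.1, and list the Day 1 data of any dosed subject who is left out.

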9. TRIAL POPULATION

9.1 Subject Disposition

Subject disposition information will be summarized for all subjects by vaccination group and dose regimen. Summaries will include the number of subjects screened, the number of subjects enrolled (ie, screened successfully), the number of subjects vaccinated, the number of subjects completing the trial, and the main reason for termination. The number of subjects per trial site/country will be summarized by vaccination group.

Subjects' data concerning screening failures will be listed.

9.2 Protocol Deviations

All potential protocol deviations will be assessed during a data review meeting. Protocol deviations due to missed or delayed assessments or in other relation to COVID-19 will be categorized as such.

The impact of protocol deviations on the analysis will be discussed during the data review meeting.

Subjects having protocol deviations and the specification of their protocol deviations will be listed including type of deviation.

9.3 Eligibility

A listing of subjects not fulfilling any inclusion or exclusion criteria will be created. Data on eligibility pre-screening, screening, and recheck will be listed.

9.4 Demographic and Baseline Characteristics

Demographic variables include age at signing informed consent, gender, child-bearing potential, and ethnic origin. Other baseline characteristics include height, weight, and body mass index (BMI) at screening and medical history at screening.

Descriptive statistics will be presented for age, height, weight, and BMI at screening. Frequency counts and percentages will be presented for gender, child-bearing potential, and ethnic origin. Demographic and baseline characteristics will be summarized for the safety analysis set and the FA set by vaccination group and dose regimen.

Medical history data will only be listed.

9.5 Prior, Ongoing and Concomitant Medications/Vaccinations

Prior, ongoing, and concomitant medications/vaccinations verbatim terms in the eCRFs will be mapped to Anatomical/Therapeutic/Chemical (ATC) class and Preferred Names using the WHODrug Global (version March 01, 2018 or higher).

Prior, ongoing, and concomitant medications/vaccinations will be listed including all information documented under this section. A flagging will show if medication/vaccination is classified as prior, ongoing, or concomitant.

Medication/vaccination definitions and their start and stop dates are as follows and imputed dates (see section 6.3) will be used for classification into each category:

- Prior medications/vaccinations are defined with a start date prior to screening and stop date before the date of first administration of the trial product.
- Ongoing medications/vaccinations are defined as any medication/vaccination used prior to screening with stop date at/after date of first administration of the trial product, or which are ongoing from screening.
- Concomitant medications/vaccinations are defined as any medication/vaccination with start date at/after date of first administration of the trial product.
- If the allocation to prior, ongoing, or concomitant is not clear, the medication/vaccination will be considered as concomitant.

Ongoing and concomitant medications/vaccinations will be summarized for each vaccination group by World Health Organization ATC class (level 2) and preferred name. These summaries will present the number and percentage of subjects using each medication. Subjects may have more than 1 medication per ATC class and preferred name. At each level of subject summarization, a subject is counted once if he/ she reported 1 or more medications at that level. Each summary will be ordered by descending order of incidence of ATC class and preferred name within each ATC class.

Prior medications/vaccinations will only be listed.

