10.3.4 Concomitant medication and Vaccinations

Concomitant medication/vaccination and significant non-drug therapies after the start of study treatment will be listed and summarized by Anatomical Therapeutic Chemical (ATC) term in contingency tables.

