16.2.3.1 Subjects Excluded from Analysis
All Subjects

Group	Subject number	Complete subject code	Excluded from FA set	Reason for exclusion
-------	----------------	-----------------------	----------------------	----------------------

PROGRAM SOURCE: tlf-###, DATA CUT-OFF DATE: DDMMYYYY

RUN DATE: DDMMYYYY hh:mm

Programming Note:

Subjects can have multiple reasons for being excluded from the analysis set (ie, not having postbaseline data by definition of the population or from having a major protocol deviation).

CONFIDENTIAL

CV-7202-104_Statistical_Analysis_Plan_V1.0.docm

CureVac AG
CV-7202-104

Statistical Analysis Plan
24 February 2022

Sponsor
Protocol Number

Clinical Study Report
Page x of y

**16.2.4.1 Demographics and Baseline Characteristics
Safety Analysis Set**

Group	Complete subject code	Age (years)	Gender	Childbearing potential	Ethnic origin	Height (cm)	Weight (kg)	BMI (kg/m ²)
-------	--------------------------	-------------	--------	------------------------	---------------	----------------	----------------	-----------------------------

*Programming Note:
Please display Gender as Female/Male, i.e. do not present the abbreviation F/M.*

PROGRAM SOURCE: tlf-###, DATA CUT-OFF DATE: DDMMYYYY

RUN DATE: DDMMYYYY hh:mm

CureVac AG
CV-7202-104

Statistical Analysis Plan
24 February 2022

Sponsor
Protocol Number

Clinical Study Report
Page x of y

**16.2.4.2 Medical History
Safety Analysis Set**

Group	Complete subject code	Diagnosis	Start date	Ongoing	End date
-------	--------------------------	-----------	------------	---------	----------

PROGRAM SOURCE: tlf-###, DATA CUT-OFF DATE: DDMMYYYY

RUN DATE: DDMMYYYY hh:mm

*Programming note:
Sort by start date within each subject.*

CureVac AG
CV-7202-104

Statistical Analysis Plan
24 February 2022

Sponsor
Protocol Number

Clinical Study Report
Page x of y

**16.2.4.3 Prior and Concomitant Medications/Vaccinations
Safety Analysis Set**

Group	Complete subject code	* Medication/Vaccination (PT)	Total daily dose	Unit/ Route/ Frequency	Start date/ Indication	Stop Date
-------	-----------------------------	----------------------------------	------------------	------------------------------	------------------------------	-----------

* P: prior, O: ongoing (starting pre-vaccination), C: concomitant (starting post-vaccination), PT: preferred term

PROGRAM SOURCE: tlf-###, DATA CUT-OFF DATE: DDMMYYYY

RUN DATE: DDMMYYYY hh:mm

*Programming note:
Sort by start date and stop date within each subject.*

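### SAP 9.5 leaves a gap between screening and Dose 1: a medication or vaccine that both starts and stops in it fits no class and defaults to concomitant

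*SAP*

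**What the plan says.** SAP 9.5 sorts each medication or vaccination record into three classes and adds a default:

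- Prior: "Prior medications/vaccinations are defined with a start date prior to screening and stop date before the date of first administration of the trial product".
- Ongoing: "any medication/vaccination used prior to screening with stop date at/after date of first administration of the trial product, or which are ongoing from screening".
- Concomitant: "any medication/vaccination with start date at/after date of first administration of the trial product".
- Default: "If the allocation to prior, ongoing, or concomitant is not clear, the medication/vaccination will be considered as concomitant".

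The class decides where the record is reported: "Ongoing and concomitant medications/vaccinations will be summarized for each vaccination group by World Health Organization ATC class (level 2) and preferred name", whereas "Prior medications/vaccinations will only be listed". The top row of Table 14.1.6 pools ongoing and concomitant use. Listing 16.2.4.3 flags each record P, O or C, and its footnote explains two of the flags as "O: ongoing (starting pre-vaccination), C: concomitant (starting post-vaccination".

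The protocol sets the scope of the summary in section 10.3.4: "Concomitant medication/vaccination and significant non-drug therapies after the start of study treatment will be listed and summarized". Protocol 10.3.2 keeps prior medication to a listing. SAP section 12 declares one change from the protocol, the dropped per-protocol sets, and nothing on medication classes.

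**The concern.** The start condition for prior and ongoing is set at screening. The stop condition for those two classes, and the start condition for concomitant, are set at first administration. Because the two dates differ, a start that falls between them is not covered, and the default then decides.

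For a course that also ended before Dose 1, the default gives the wrong answer: use known to have finished before vaccination is reported with use after it. Table 14.1.6 is the only medication summary in the SAP's table index, and the groups are small, so one subject can visibly move a row. For a course that continued past Dose 1, inclusion in the table is right, but a C flag would state that it began after vaccination when it began before.

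**Working it through.** The plan gives no figure to reproduce. The check is logical, followed by simple arithmetic for size.

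**Inputs.** The class rules and default are those of SAP 9.5. Screening (Visit 2) falls 30 to 1 days before vaccination and includes a medication assessment (Protocol 9.4.2). Medication is assessed again at Visit 3 (Protocol 9.4.3). Pre-screening (Visit 1) may fall up to 90 days before vaccination (Protocol 9.4.1). SAP section 7 labels Visit 2 as screening, so a gap of up to 30 days is the natural reading; it would be up to 90 if pre-screening were meant. Numbers vaccinated are 16, 16, 10 and 11 (SAP 6.4).

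**One record with complete dates.** Screening Day -30, start Day -10, stop Day -7.

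1. Prior? No. The start is not before screening.
2. Ongoing? No. There was no use before screening and none under way at screening.
3. Concomitant by definition? No. The start is before first administration.
4. The default remains, and gives concomitant.

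**All cases.** Every start/stop pair from 120 days before to 60 days after Dose 1 was classified under SAP 9.5 and under a single cut at Dose 1. Results for screening 30 days before Dose 1:

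| Start | Stop | SAP 9.5 | Cut at Dose 1 only | Possible pairs |
|---|---|---|---|---|
| before screening | before Dose 1 | prior | prior | 6795 |
| before screening | at/after Dose 1 | ongoing | ongoing | 5490 |
| screening to before Dose 1 | before Dose 1 | none, default concomitant | prior | 465 |
| screening to before Dose 1 | at/after Dose 1 | none, default concomitant | ongoing | 1830 |
| at/after Dose 1 | at/after Dose 1 | concomitant | concomitant | 1891 |

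The gap counts follow directly: 30 + 29 + ... + 1 = 465, and 30 start days × 61 stop days = 1830. They count possible date combinations, not expected records. The same single gap appears with screening 1 or 90 days before Dose 1.

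The check treats the second limb of ongoing as use under way at screening that is still running at Dose 1. If it meant merely in use at screening, a drug started before screening and stopped before Dose 1 would meet both prior and ongoing. A single cut at Dose 1 removes that ambiguity too.

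**Size of one misplaced subject in a Table 14.1.6 row.**

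- 1 µg or 2 µg group: 1/16 = 6.25%, shown as 6.3 points.
- 5 µg group: 1/10 = 10.0 points.
- Rabipur group: 1/11 = 9.1 points.
- Total column: 16 + 16 + 10 + 11 = 53, and 1/53 = 1.9 points.

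The table counts a subject once per level, so these are the most that one subject can add to a row. They apply only if the subject has no other record in that row with use on or after Dose 1.

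**The case against.** The strongest defence is that the default is written for allocations that are not clear. SAP 6.3 describes imputing missing or incomplete medication dates for this classification and takes a conservative approach throughout. On that reading the default serves uncertain dates, and a record with complete dates is undefined rather than unclear. The listing footnote even suggests that the intended split is at vaccination. This stands as a caution about what would actually be programmed. It does not close the gap: each record must carry one of three flags, none of the definitions fits, and no other rule exists. Calling the record ongoing would not help, because ongoing records enter the same table.

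A reader might infer that the whole classification is cut at screening. It is not; only the start condition of prior and ongoing is.

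A reader might also infer that the reactogenicity assessment, the primary objective, is distorted through analgesic or antipyretic use. The documents do not support this. Table 14.1.6 has no time window and pools about 24 months of follow-up, so it could not isolate use in Days 1 to 8 even with correct classes. Solicited event grades come from the diary (SAP 11.2.1).

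The protocol also limits how often the gap can matter. Exclusion criterion 2 restricts other vaccines around enrolment and trial vaccination, healthy subjects must not need regular or frequent medication (6.1), and prophylactic medication is not allowed (8.10). Sporadic use and unplanned vaccination remain possible. Finally, Listing 16.2.4.3 prints start and stop dates, so a careful reader can spot a wrong flag.

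**Conclusion.** The gap is real and follows from the wording of SAP 9.5 with complete dates. As written, a course confined to the interval from screening to Dose 1 goes to concomitant, enters Table 14.1.6 against Protocol 10.3.4, and receives a flag that the listing's own footnote makes untrue. A course begun in the gap and continued past Dose 1 is correctly tabulated but, if sent to the default, wrongly flagged.

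The consequence is minor. The documents do not show how many records fall in the gap, and the point shifts above are conditional maxima per subject and row. They assume that the table denominators equal the numbers vaccinated in SAP 6.4. No primary or secondary endpoint uses these classes. This is a worthwhile correction to a descriptive table and a listing flag, and no more.

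**What to change.** Define all three classes in SAP 9.5 by the date of first vaccination alone:

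- Prior: stopped before it, whatever the start date.
- Ongoing: started before it, and either stopped on or after it or still continuing.
- Concomitant: started on or after it.

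Apply the concomitant default only when the dates, after any imputation under SAP 6.3, cannot show that use ended before first vaccination.

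Each dated record then has exactly one class. On the reading used in the check, no record outside the gap changes class. The result agrees with the Listing 16.2.4.3 footnote and Protocol 10.3.4. The cost is a few sentences in the SAP and the matching derivation in the programs. No new data are needed.
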